2.2. OVERALL STUDY PLAN

PERSIST-AVR is a prospective, randomized (1:1), adaptive, open, multi-center, international study.

The trial plans for an inclusion period of approximately 30 months at approximately 60 international sites where the Perceval is commercially available. Subjects will be followed for 5 years. Total study duration of approximately 7.5 years is expected. Subjects will be evaluated at screening (the preoperative assessments will be considered as baseline), at discharge visit following prosthesis implant, between one and three months, at 1 year, and annually up to 5 years.

Study flowchart is graphically reported in Figure 1.

Figure 1: Study Flowchart

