13.1.2. Adverse Events Incidences

The incidence of AE is defined as the number of subjects with occurrence of this AE during the period of interest. The incidence rate (CIR for crude incidence rate) of an AE is defined as the number of subjects with occurrence of this AE during the period of interest divided by the total number of subjects n in the respective group (e.g., treatment group).

The incidence, incidence rate, the number of events and the percentage of events (related to the total number of events) will be summarized by AE term over the entire study post-implant period (from Day 1) and during the early and late phases (section 18.12). For the late events, the incidence rate will be calculated on the number of late patients only.

In addition, safety summaries will be done according to the following plan:

- Intraprocedural and periprocedural (within 72 hours) serious adverse events regardless of relationship with the device.

- All valve and procedure relevant (according to CEC adjudication) serious adverse event composite endpoints and their components as specified in VARC-2 guidelines (and reported in section 18.12):
 - Early safety at 30 days
 - Clinical efficacy after 30 days
 - Time related valve safety annually up to 5 years
- Serious device related (according to CEC adjudication) adverse events up to 5 years (from day 1 up to Day 1826)
- Postoperative site-reported unexpected serious adverse device effect (USADE)
- Site-reported relationship to procedure, device, drug/medication, or other Protocol Required Assessment (section 18.12)
- All late serious adverse events will be analyzed according to a constant hazard model: the linearized rates will be calculated as:
 - total number of late events divided by the total time under evaluation after 30 days (late patient-years).
 - number of patients with at least one late event divided by the total time under evaluation after 30 days (late patient-years).
- The incidence, incidence rate, the number of events and the percentage of Pacemaker (PM) implantation according to:
 - time of occurrence (overall, early, late and up to 1 year), and
 - relationship to device and procedure.

In addition, time-to-event methods (section 5.2) will be used to summarize the time to onset of the following events:

- deaths (overall, cardiovascular, and non-cardiovascular),
- explants and
- all main cardiovascular SAEs:
 - Bleeding,
 - SVD,
 - endocarditis,
 - valve thrombosis,
 - thromboembolic events,
 - stokes,

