18.12. DATA DERIVATIONS

Table 8 : Data derivation rules

Derived variable	Derivation algorithm
Consented subject	Yes if filled date of consent No, otherwise.
Enrolled subject	Yes if filled date of consent AND patient is not a failure to implant (termination reason= FAILURE TO MEET RANDOMIZATION CRITERIA) No, otherwise.
ITT subject	Yes if Randomization date not empty No, otherwise.
mITT subject	Yes if ITT and the valve is a study valve (as listed in CRF). In case of "other" values, they have to be checked one by one with PM. No, otherwise.
Adherence to Randomization allocation	Yes if "Was the randomized valve implanted?" at first attempt=Yes No, otherwise.
SAF subject	Yes if Randomization and Implant dates not empty No, otherwise.
PP subject	Yes if 
 - Randomization and Implant dates not empty - Adherent to randomization - no major protocol violation (as reported in CRF field). No, otherwise.

Derived variable	Derivation algorithm
Operating room suite time (min)	Implant, Surgical time: Finish time – Start time
Skin-to-skin time (min)	Implant, Surgical time: Finish time – Start time
Extracorporeal circulation time (min)	Implant, Surgical time: Finish time – Start time
Cross clamp time (min)	Implant, Surgical time: Finish time – Start time
ICU stay (minutes)	Intensive Care Unit: [Date/Time of ICU Discharge] - [Date/Time of ICU Admission] If time of ICU discharge is missing it will be set at 23:59 If time of ICU Admission is missing it will be set at 00:00
ICU stay (days)	ICU stay (minutes) / 1440
Time to SAE	Serious Adverse Event (SAE): SAE start date – Surgery date +1
Early, Late SAE	EARLY if Time to SAE ≤ 30 days LATE if Time to SAE > 30 days

Derived variable	Derivation algorithm
Early safety (at 30 days)	
Serious Adverse Event (SAE):
 
YES if at least one (Time to SAE <=30 days) per CEC:
 
 - All-cause mortality - All stroke disabling and nondisabling - Life-threatening bleeding - Acute kidney injury—Stage 2 or 3 (including renal replacement therapy) - Coronary artery obstruction requiring intervention - Major vascular complication - Valve-related dysfunction requiring repeat procedure (BAV, TAVI, or SAVR): SVD and Aortic regurgitation requiring re-intervention 
NO, otherwise

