MACCE @ n year (Yes/No)	
CEC adjudication of Serious Adverse Event (SAE), Valve re-intervention:
 
YES if at least one per CEC:
 
 - Death (Time to SAE <=n*365.25 days) - Myocardial infarction (Time to SAE <= n*365.25 days) per CEC - Stroke (Time to SAE <= n*365.25 days) per CEC - Reintervention (Time to SAE <= n*365.25 days) 
NO, otherwise

PM implant	
SAE FORM – TREATMENT
 
Yes if:
 
 - Was a pulse generator implanted? = YES - If yes, specify = Pacemaker 
NOTE: PM implant will be classified as intraoperative, early or late according to the date of PM implant (not the AE start date)

Derived variable	Derivation algorithm
Last exposure date	
Study Termination, Serious Adverse Event (SAE):
 
 1. For explant of investigational device: date of explant 2. For dead subjects: date of death 3. For alive and not explanted subjects: 
 - Date of termination - If there is no date of termination, the last available FU date (including discharge) or the last SAE date (occurrence date), whichever occurs later. - If there is no follow-up and no adverse events : date of surgery or date of randomization, whichever occurs later.
Last study date	
Study Termination, Serious Adverse Event (SAE):
 
 1. For dead subjects: date of death 2. For alive subjects: 
 - Date of termination - If there is no date of termination, the last available FU date (including discharge) or the last SAE date (occurrence date), whichever occurs later. 
If there is no follow-up and no adverse events : date of surgery or date of randomization, whichever occurs later.

Study length (days)	
Study termination, Subject Information:
 
Last study date – Enroll Date+1

Extent of exposure (days)	
Last exposure date-surgery date+1

Late patients	
Subjects with more than 30 FU days of exposure

Patient-years	
Cumulative Study length (days)/365.25

Derived variable	Derivation algorithm
Early patient-years	Cumulative Study length (days) up to 30 days/365.25
Late patient-years	Cumulative Study length (days) from 31st day/365.25. Subjects with less than 31 FU days do not contribute to the late patient-years

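### The patient-based linearized rate for late serious adverse events keeps time after the first event in its denominator, so this one descriptive rate is not the constant-hazard estimate that SAP 13.1.2 presents

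*SAP*

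**What the plan says.** SAP 13.1.2 states the model: "All late serious adverse events will be analyzed according to a constant hazard model". Two linearized rates follow. The first is the "total number of late events divided by the total time under evaluation after 30 days (late patient-years". The second has a different numerator and the same denominator: "number of patients with at least one late event divided by the total time under evaluation after 30 days (late patient-years".

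Table 8 in SAP 18.12 supplies the pieces:

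- An event is late by the rule "LATE if Time to SAE > 30 days", with time counted from surgery.
- Late patient-years are "Cumulative Study length (days) from 31st day/365.25".
- Study length is "Last study date – Enroll Date+1". The last study date is the date of death or of termination; if there is no termination date, it is the later of the last follow-up and the last SAE.

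None of these definitions ends a patient's time at the first late event. SAP 2.2 sets the horizon: "Subjects will be followed for 5 years". SAP 4.4 repeats the analysis each year from year 2 to year 5.

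The setting is descriptive (SAP 13). Section 13.1.2 also applies the time-to-event methods of SAP 5.2 to death, explant, the main cardiovascular SAEs, hospitalizations and first pacemaker implant.

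**The concern.** Under a constant hazard, a count divided by person-time estimates the hazard only if the person-time is time at risk of adding to the count. For total events, all late follow-up qualifies. For patients with at least one event, risk ends at the first event, but the SAP keeps the rest of that patient's follow-up in the denominator.

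Two things follow for this rate:

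- **It is too low.** The shortfall grows with the event frequency and with the length of follow-up. The arm with more events is understated more, so a reader who divides one arm's rate by the other's sees a ratio too close to 1.
- **It drifts.** The same constant hazard gives a lower figure at each successive annual analysis, so figures from different cutoffs cannot be set side by side.

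The rate applies to all late SAEs. The effect would be largest for common, non-terminal ones, where patients stay under observation for years after the first event.

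**Working it through.** The plan states no linearized rate, so there is no figure to reproduce. The check compares the SAP's estimator with the hazard that it is meant to estimate.

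**Inputs from the documents**

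- Constant hazard, and the numerator and denominator of the second rate: SAP 13.1.2.
- Person-time from day 31 to the last study date: SAP 18.12, Table 8.
- Follow-up of 5 years: SAP 2.2. Late time per patient is T = 5 − 30/365.25 = 4.92 years.
- Accrual of about 30 months (SAP 2.2), with the primary analysis 12 months after accrual ends (Protocol 8.1). Follow-up then runs from 1 to 3.5 years, and late time from a = 0.918 to b = 3.418 years, mean 2.17.

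**Assumptions**

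- First-event hazards λ of 0.02 to 0.20 per year. The documents give none for frequent late SAEs.
- Uniform accrual, and no deaths in the main table.
- Late time counted from surgery. Table 8 builds study length from the enrolment date; that is a separate matter and does not change the argument here.

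**Formulas**

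- SAP rate, fixed T: (1 − exp(−λT)) / T.
- SAP rate, late time uniform on (a, b): {1 − [exp(−λa) − exp(−λb)] / [λ(b − a)]} / [(a + b)/2].
- Rate with time stopped at the first event: (1 − exp(−λT)) / [(1 − exp(−λT))/λ] = λ.

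**Worked case, λ = 0.10 per year**

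- 5 years: exp(−0.4918) = 0.6115, so 0.3885 of patients have an event. The SAP rate is 0.3885/4.918 = 0.0790, which is 21.0% low. Mean time to first event or end of follow-up is 0.3885/0.10 = 3.885 years, and 0.3885/3.885 = 0.10.
- Primary cutoff: exp(−0.0918) = 0.9123 and exp(−0.3418) = 0.7105. Then 1 − 0.2018/0.25 = 0.1928, and 0.1928/2.168 = 0.0889, which is 11.1% low.

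**Results, no deaths**

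| True λ per year | SAP rate, 5 years | Bias | SAP rate, primary cutoff | Bias |
|---|---|---|---|---|
| 0.02 | 0.0190 | −4.8% | 0.0195 | −2.4% |
| 0.05 | 0.0443 | −11.3% | 0.0471 | −5.8% |
| 0.10 | 0.0790 | −21.0% | 0.0889 | −11.1% |
| 0.20 | 0.1273 | −36.4% | 0.1592 | −20.4% |

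SAP 4.1 directs the primary analysis at safety up to the 12-month visit. If the late-SAE table is also cut there (T = 0.918), the biases are −0.9%, −2.3%, −4.5% and −8.6%.

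**Deaths.** With death hazard μ, the SAP rate is {λ(1 − exp(−(λ+μ)T))/(λ+μ)} / {(1 − exp(−μT))/μ}. At 5 years and λ = 0.10, the bias is −20.5% for μ = 0.03 and −20.1% for μ = 0.06. At λ = 0.20 it is −35.6% and −34.8%. The death assumption matters little.

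**Ratio a reader might form, 5 years, no deaths**

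| Control λ per year | True 1.5 appears as | True 2.0 appears as |
|---|---|---|
| 0.02 | 1.46 | 1.91 |
| 0.10 | 1.34 | 1.61 |
| 0.20 | 1.23 | 1.37 |

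**Rare events.** Protocol 6.2 gives late stroke as 0.8% and late major paravalvular leak as 0.3% in the pooled earlier trials. Even if these are read as yearly hazards, the 5-year bias is 1.9% and 0.7%. Read as cumulative proportions, it is smaller still.

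**Simulation** (2,000,000 patients per setting, μ = 0.03, 5 years). At λ = 0.02, 0.10 and 0.20, the SAP denominator gave 0.0190, 0.0794 and 0.1288. Stopping time at the first event gave 0.0200, 0.0999 and 0.2001. The total-event rate kept a true ratio of 2.0 at 2.00.

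**The case against.** The case on the other side has four parts.

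1. **No arm ratio of these rates is planned.** SAP 13.1.2 attaches no ratio, test or interval to them, and SAP 13 is descriptive. This stands. The ratios above are what a reader would get by dividing two printed figures, not outputs of the plan.

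2. **The same events are analysed soundly elsewhere.** The total-event rate is valid on total late patient-years and covers all late SAEs. Kaplan-Meier, log-rank and hazard-ratio analyses cover hospitalizations, arrhythmias and conduction disorders, bleeding, stroke, endocarditis and other main events. This also stands. A reader might infer that the plan hides or shrinks any late safety excess in one arm. The documents do not support that: the distortion is confined to one of several summaries.

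3. **The large percentages rest on assumed hazards.** This is correct. The documents give no late rate for hospitalizations or arrhythmias, and the late rates that they do give imply a bias of about 2% or less. Death is unaffected because person-time ends there, and explant is affected only slightly where it ends follow-up.

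4. **The denominator is stated openly, so a label would do.** This holds only in part. Calling the quantity patients with an event per patient-year observed would remove the conflict with the constant-hazard heading. It would not remove the dependence on follow-up length, so figures from different annual analyses would still not be comparable.

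**Conclusion.** The concern holds for one descriptive quantity. The second linearized rate in SAP 13.1.2 does not estimate the constant hazard under which it is presented. It is biased low and depends on follow-up length, and comparisons formed from it move toward 1.

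The direction follows from the SAP's own definitions. The size rests on assumed hazards, a hazard that is in fact constant and, for the primary cutoff, uniform accrual. It is material only for frequent, non-terminal late SAEs, or for all late SAEs pooled.

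Nothing here touches the primary endpoint, the interim decisions, the total-event rate or the planned time-to-event analyses. A reading that the trial's safety conclusions as a whole are biased toward no difference goes beyond what the documents show.

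**What to change.** In SAP 13.1.2, change the denominator of the second rate only: late patient-years from day 31 after surgery to the date of the patient's first late event of that type, or to end of follow-up if there is none. Keep total late patient-years for the total-event rate. Add the matching entry to Table 8 beside the existing definition of late patient-years.

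The cost is one line of SAP text and one exposure variable per event type in programming. Event dates and last study dates are already collected, so no new data are needed.

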6.2 AVAILABLE CLINICAL DATA

From April 2007 to February 2008 a Pilot trial was conducted to demonstrate the safety of the Perceval valve at 30 days post implant in 30 subjects affected by aortic valve disease requiring valve replacement. Female patients were 73% of the enrolled population and the mean age was 80.4 ± 3.8 years. The patients were followed for 5 years and at the latest follow up 22 patients were alive with a freedom from death of 71.31%. No incidence of stroke, dislodgment or structural valve deterioration were reported [15]. At 5 years overall mean gradient was 9.3 mmHg and the overall effective orifice area was 1.7 cm^2 .

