10.1.6 SUMMARY STATISTICS

Descriptive statistics will be calculated using as reference the number of subjects in the relevant analysis population (any exception will be specified) according to the nature of each parameter as follows:

- For quantitative (continuous) parameters: Number of subjects with available and missing data, mean, standard deviation (SD), median, quartiles (Q1-Q3) and extreme values [Minimum; Maximum];
- For qualitative (discrete) parameters: Number of subjects and frequency (percentage);
- For Time-to-event variables: Cumulative freedom from events will be evaluated using the method of Kaplan-Meier. The degree of uncertainty in each actuarial analysis will be expressed with 95% confidence limits. The 95% confidence interval bounds for the cumulative freedom will be calculated per the method proposed by Greenwood [25]. Comparison of curves among arms will be performed with the log-rank test. Kaplan-Meier graphs will be presented along with the number of patients-at-risk at exact time points. Covariate analyses will be based on the proportional hazards model. Arms will be compared using multivariate Cox proportional hazards regression. The hazard ratio (95% C.I.) will be presented.
- For Bayesian analyses: posterior means, standard deviations, and 95% credible intervals will be reported.

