18 HANDLING OF TRIAL DISCONTINUATIONS

18.1 HANDLING OF SUBJECTS' TEMPORARY TREATMENT DISCONTINUATION OR TERMINATION

For all subjects reaching the end of the trial (completed 5 year visit, death, or explant) or in case of premature withdrawal as described in section 8.5.5 (lost-to-follow-up, or subject's decision) a trial termination form will be filled out in order to document the date and reason for discontinuation. Subjects who had their valves explanted will still have to be followed at least till 1 year primary endpoint.

Every attempt must be made to have all subjects complete the follow-up visit schedule. A subject will be considered lost to follow-up when all efforts to obtain information are unsuccessful. At a minimum, the effort to obtain information must include attempts to make three contacts via phone, one certified letter should be sent to the subject's last known address. Phone contacts and copy of the letter must be documented/available in the subject's medical record.

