5.2. DESCRIPTIVE STATISTICS

Descriptive statistics will be calculated using as reference the number of subjects in the relevant analysis population (any exception will be specified) according to the nature of the data as follows:

- Continuous variables: number of non-missing observations, arithmetic mean, standard deviation, minimum and maximum values, median and quartiles. If there are less than 5 observations, only the number of non-missing observations, arithmetic mean, median, minimum and maximum will be presented.
- Categorical variables: Number of missing and non-missing observations the relevant percentage on the analysis population. In case of subcategories, the relative frequencies will be calculated on the basis of the subjects in the subcategory, in this case a footnote will be added explaining the different denominators.
- Time-to-event variables: number of non-missing observations, minimum, first quartile, median including 95% confidence interval, third quartile, and maximum. For calculating the survival estimate CI bounds the log-log transformed estimate of CI bounds will be used. In addition, Kaplan-Meier estimates and plots will be provided with:
 - the 95% confidence interval bounds calculated per the method proposed by Greenwood⁸
 - the respective number of patients at risk and Kaplan-Meier estimates at different time points (at least every 5 months or more frequently)
 - the median and its 95% confidence interval.
 - the log-rank test p-value
 - the Hazard Ratio (HR), its 95% confidence interval and the relevant p-value.

Subjects ongoing and who are free from event at the analysis cut-off date will be censored at the analysis cut-off date. Subjects who have discontinued without an event will be censored at the date of discontinuation.

- For Bayesian analyses: posterior means, standard deviations, and 95% credible intervals will be reported.

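### Late non-fatal events and cause-specific death have Kaplan-Meier as their only time-to-event estimator up to 5 years; if deaths are censored, as the plan implies, late absolute risks are overstated

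*SAP*

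**What the plan says.** SAP 13.1.2 first plans crude incidence rates and linearised late rates, then adds: "In addition, time-to-event methods (section 5.2) will be used to summarize the time to onset of the following events". The list begins with "deaths (overall, cardiovascular, and non-cardiovascular" and goes on to explants, bleeding, SVD, endocarditis, valve thrombosis, thromboembolism, stroke, leaks, myocardial infarction, hospitalisations and first pacemaker implant.

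The estimator is the same in both documents. Protocol 10.1.6: "Cumulative freedom from events will be evaluated using the method of Kaplan-Meier". SAP 5.2: "In addition, Kaplan-Meier estimates and plots will be provided with" Greenwood limits, numbers at risk, a log-rank p-value and a hazard ratio.

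SAP 5.2 has two censoring rules: "Subjects ongoing and who are free from event at the analysis cut-off date will be censored at the analysis cut-off date" and "Subjects who have discontinued without an event will be censored at the date of discontinuation". Neither mentions death.

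Two other places bear on death. Protocol 18.1 requires a termination form, giving the date and reason for discontinuation: "For all subjects reaching the end of the trial (completed 5 year visit, death, or explant", as well as for premature withdrawals. SAP 18.12 (Table 8) sets the last study date of a dead subject to the date of death. Follow-up is 5 years, with yearly analyses at 2, 3, 4 and 5 years (SAP 4.4).

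**The concern.** A patient who has died can no longer have SVD, endocarditis or a hospitalisation. If death is treated as ordinary censoring, Kaplan-Meier in effect assumes that the dead would have gone on to have events at the same rate as the living. 1-KM then estimates risk in a hypothetical population in which nobody dies, and that is higher than the proportion of patients who will have the event. Cardiovascular and non-cardiovascular death raise the same problem, because each prevents the other.

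At stake are the absolute 2- to 5-year probabilities and curves for valve events, which readers will take as patient-level risks of each valve. The excess grows with follow-up and with mortality. If mortality differs between the arms, the excess differs too.

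**Working it through.** The documents give no figure for these summaries, so there is none to reproduce. The check has two parts.

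**1. Is death censored?** SAP 5.2 is silent. Protocol 18.1 puts death on the form that dates discontinuation, SAP 5.2 censors event-free discontinued subjects on that date, and SAP 18.12 ends a dead subject's study time at death. Together these make censoring at death the natural reading. It remains an inference.

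**2. How large is the excess?**

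Death hazards *m*, converted as constant rates from Protocol 6.2:
- Pilot (30 patients), 5-year "freedom from death of 71.31"%: −ln(0.7131)/5 = 0.0676 per year.
- Matched series, 2-year survival 93% and 91%: −ln(0.93)/2 = 0.0363 and −ln(0.91)/2 = 0.0472. The value 0.04 used below lies between them.
- Multicentre series of 314, 1-year survival 90.5%: −ln(0.905) = 0.0998.
- 0.02 is an assumed low end.

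The event hazard *l* = 0.01 per year is an assumption. The relative excess hardly depends on it: at the pilot's mortality the 5-year ratio is 1.178 for *l* = 0.002 and 1.174 for *l* = 0.03.

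Formulas for constant hazards at time *t*:
- 1-KM with death censored = 1 − exp(−*l t*)
- Cumulative incidence with death competing = *l*/(*l*+*m*) × [1 − exp(−(*l*+*m*)*t*)]

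At 5 years, 1-KM = 1 − exp(−0.05) = 4.877%.
- *m* = 0.04: (0.01/0.05) × [1 − exp(−0.25)] = 4.424%. Excess 0.45 points, ratio 1.10.
- *m* = 0.0676: (0.01/0.0776) × [1 − exp(−0.388)] = 4.144%. Excess 0.73 points, ratio 1.18.

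Across *m* = 0.02 to 0.0998:

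| Situation | 1-KM ÷ cumulative incidence |
|---|---|
| Constant hazard, 5 years | 1.05 to 1.27 |
| Constant hazard, 1 year | 1.01 to 1.05 |
| Hazard rising as *t*² (SVD-like), 5 years | 1.08 to 1.45 (1.29 at pilot mortality) |
| Early event (assumed 8% within 7 days; 30-day mortality 1.8-3.4%) | 1.002 to 1.004 |
| All-cause death | 1 exactly |

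The rising-hazard row integrates *h*(*t*)·exp(−*H*(*t*))·exp(−*mt*) numerically, with *h* = *ct*², *H* its cumulative hazard, and *c* set so that 5-year 1-KM is 5%. At the pilot's mortality the cumulative incidence is then 3.89%.

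Cause-specific death: split the pilot's mortality equally between the two causes (an assumption). Each 1-KM is 1 − exp(−0.0338 × 5) = 15.55%. The two sum to 31.1%, but all-cause mortality is only 100 − 71.31 = 28.7%.

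**The case against.** The strongest reply is that the plan never says deaths are censored. SAP 5.2 does not mention death, Protocol 8.5.5 does not list it among the reasons for discontinuation, and Protocol 18.1 distinguishes it from premature withdrawal. A reader might take censoring at death as a stated rule, and the documents do not support that. What stands is that the rule is missing, the surrounding text points to censoring, and Kaplan-Meier is the only time-to-event estimator whichever rule was intended.

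Three broader readings also fail:
- **Every listed event is overstated.** All-cause death is on the list and is unaffected. First-week events move by less than 0.5% relative, and 1-year estimates by 1-5%. The pacemaker endpoint in Protocol 8.5.8 runs only to 1 year.
- **Nothing in the SAP is free of the problem.** The crude incidence in SAP 13.1.2 divides by all subjects in the group, so for events counted over the whole post-implant period the dead stay in the denominator. It does not have this inflation, although it ignores incomplete follow-up and gives no curve. Linearised rates are not probabilities.
- **The comparison of arms is invalid.** With death censored, the log-rank test and hazard ratio are valid for the cause-specific hazard. Gray's test addresses a different question, in which mortality enters the comparison; using it is a choice of estimand.

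Advanced age is not an eligibility rule either: Protocol 8.5.2 asks only for legal minimum age. The mortality used here comes from earlier cohorts with mean ages near 80, and the 18% figure from one of only 30 patients. These are secondary summaries that SAP 13 calls descriptive, and no success criterion depends on them.

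**Conclusion.** The point holds for late non-fatal events and for cardiovascular and non-cardiovascular death, as a matter of absolute risk in the 2- to 5-year analyses. On the natural reading that deaths are censored, an event with a 5-year 1-KM of 4.88% is overstated by about 0.5 points (10% relative) at a 4% yearly death hazard, and by about 0.7 points (18%) at the pilot's mortality. For a late-rising event such as SVD the relative excess is larger, 8-45% over the range examined. These sizes are illustrative: they assume constant or *t*² hazards, an assumed event rate, and mortality carried over from earlier cohorts.

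The primary MACCE endpoint includes all-cause death and is untouched. This does not threaten the trial's main conclusion, but it is worth correcting before long-term valve-event probabilities are reported.

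**What to change.** Amend SAP 5.2 and 13.1.2 as follows:

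1. State that death is a competing event for every non-fatal time-to-event endpoint, and that cardiovascular and non-cardiovascular death compete with each other.
2. Report Aalen-Johansen cumulative incidence by arm for these endpoints, mainly at the 2- to 5-year analyses. Keep Kaplan-Meier as a secondary display for comparison with the valve literature.
3. Keep log-rank and Cox, labelled as cause-specific comparisons. Gray's test is optional.
4. State how explant is handled. Protocol 18.1 requires follow-up of explanted subjects only to at least 1 year, so explant may also cut off later valve events. If it is treated as competing, an explant done for the event itself must count as the event: the time-related SVD derivation in SAP 18.12 requires a repeat procedure, so the same operation could otherwise be both event and competitor. Explant is also an endpoint in its own right.
5. Leave all-cause death and MACCE on Kaplan-Meier.

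The cost is an SAP amendment, a standard software option and a few extra curves. The new figures will differ slightly from those in older valve reports, which is the reason to keep the Kaplan-Meier display.
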